Objectives: The objective of this study is to evaluate if enteral absorption improves in subjects with SBS following therapy with pancreatic enzymes. Enteral absorption will primarily be assessed using stool coefficient of fat absorption (CFA). Secondary objectives of the study include measurement of coefficient of nitrogen absorption (CNA) and stool bomb calorimetry (BC) before and after pancreatic enzyme administration. A subset of subjects will also have enteral absorption measured using the malabsorption blood test (MBT) before and after pancreatic enzyme administration.

Study Design: This is an interventional study of subjects with SBS who will be evaluated before and after pancreatic enzyme administration. A subset of subjects will have the MBT performed before and after pancreatic enzyme administration as a measure of enteral fat absorption.

Setting/Participants: This outpatient study will be conducted at CHOP. Approximately, sixteen subjects with SBS between the ages of 4.0 and 17.9 years and ten adult subjects with SBS between the ages of 18 and 75 years will be enrolled. Only adult subjects have the option to be part of the subset that has the MBT.

Study Interventions and Measures: Subjects with SBS will be evaluated both on and off Creon™, a pancreatic enzyme medication. Enteral absorption will be measured before and after pancreatic enzyme administration. Enteral absorption will be measured using three methods: CFA, CNA, and BC. A subset of adult subjects will also have the MBT before and after pancreatic enzyme administration. Subjects with SBS have significant malabsorption and have several proposed mechanisms of functional pancreatic insufficiency. The longterm goal is to determine if pancreatic enzymes improve enteral absorption in patients with SBS, it may allow parenteral nutrition to be weaned and improve both their morbidity and mortality.

PROTOCOL SYNOPSIS

Study Title	The Use of Pancreatic Enzymes in Short Bowel Syndrome
Funder	AbbVie Inc.
Clinical Phase	Phase II – This is an open-label intervention therapeutic exploratory study
Study Rationale	
Patients with short bowel syndrome (SBS) have a high mortality rate that is mainly attributed to complications from central venous access and parenteral nutrition¹. In 2012, Squires et al¹ published the largest retrospective review to date that described outcomes for patients with SBS at fourteen centers in the United States. The study showed that over a 5-year period, the mortality rate was 27%. Central venous access and parenteral nutrition also expose patients to an increased risk of several morbidities, including gallstones, cholestatic liver disease, glucose instability, deep vein thromboses, bone disease, and emboli. The ultimate goal in clinical management of patients with SBS is to wean off of parenteral nutrition and establish enteral autonomy. This goal can be difficult to achieve due to the significant malabsorption that occurs in SBS. Madsen et al² studied a cohort of subjects with short bowel syndrome, high stool output, and high fecal energy losses and demonstrated that they had a low coefficient of fat absorption of about 48%. This study demonstrates how significant malabsorption can be in patients with SBS and therefore highlights the challenge that clinicians face in attempting to minimize parenteral nutrition use. There are few medical therapies that improve absorption in patients with SBS. To date, teduglutide, a glucagon-like-peptide 2 (GLP-2) analog, is the only medication that has been clinically shown to improve intestinal adaptation and allow parenteral nutrition to be weaned in adults³. This drug shows great promise, but there are several concerns, such as increased risk of cancer and a loss of response with drug withdrawal.
 
Pancreatic enzymes have been successful in improving enteral absorption in several patient populations, most notably in cystic fibrosis^{4,5}. The impact of pancreatic enzymes on enteral absorption has not been evaluated in patients with SBS and will be the main focus of this study. Maximizing absorption to reduce parenteral nutrition needs in this patient population will be essential in reducing morbidity and mortality.
 
The main objective of this study is to demonstrate if therapy with pancreatic enzymes will improve enteral fat absorption in patients with SBS. We hypothesize that patients with SBS are functionally pancreatic insufficient as a result of their intestinal resection for the following reasons: 1) decreased cholecystokinin (CCK) secretion and impaired enteroendocrine hormone secretion, 2) rapid intestinal transit, 3) high intestinal intraluminal volume, and 4) gastric acid hypersecretion.
 
Exploratory aspects of the study also address the changes that nutrient absorption will have on intestinal adaptation and enteroendocrine hormone signaling. In our study, we will measure several hormone and enteroendocrine


hormone concentrations at baseline and following administration of pancreatic enzymes both as evidence for proper digestion and as markers of intestinal adaptation.

SBS is a life threatening disease process with a paucity of noninvasive therapies that directly improve enteral absorption and improve patient outcome. If pancreatic enzyme medication is found to improve enteral absorption, this study will increase the clinical use of pancreatic enzymes in patients with SBS. This study will also provide further information on the mechanisms of malabsorption in patients with SBS, which could facilitate identification of other therapeutic targets to improve enteral absorption. It will provide the framework for larger studies to improve enteral absorption in patients with SBS.

Study Objective(s)	Primary: The primary objective of this study will be to determine if enteral absorption improves in subjects with SBS following therapy with pancreatic enzymes. Patients with SBS have significant fat malabsorption for several reasons ² . Lipid malabsorption in SBS occurs due to bowel resection, diluted pancreatic enzymes, altered enteroendocrine hormone signaling, acid hypersecretion, and rapid intestinal transit ⁶ . Pancreatic enzymes play a major role in enteral fat absorption. We propose that administering pancreatic enzymes to subjects with SBS will improve absorption of enteral nutrition. The primary hypothesis of this study is: H1: Pancreatic enzyme medication will improve enteral fat absorption in subjects with SBS, which will be indicated by an improved stool coefficient of fat absorption (CFA). Secondary: A secondary hypothesis of this study will aim to further characterize the effect that pancreatic enzyme medication will have on global nutrient absorption. H2: Coefficient of nitrogen absorption (CNA) and bomb calorimetry (BC) will detect changes in enteral protein absorption and stool energy losses, respectively, before and after therapy with pancreatic enzymes. We will address the unique difficulty of measuring enteral fat absorption in subjects with SBS. Fat absorption in a subset of subjects will be measured using the MBT. CCK concentration will also be measured in this subset as an additional area of exploration, as CCK plays a pivotal role in pancreatic enzyme secretion ⁶ . Additionally, we will explore the effect that improved nutrient absorption will have on intestinal adaptation by measuring changes in markers of intestinal mass and hormone levels.
---------------------------	---

H3: The MBT will detect changes in enteral fat absorption before and after therapy with pancreatic enzyme medication on a subset of subjects. It will also help characterize the degree of pancreatic insufficiency in subjects. Baseline serum CCK concentration and serum CCK concentration following pancreatic enzyme therapy will also be determined in this subset.

H4: By promoting lipid digestion and release of free fatty acids, pancreatic enzymes will promote intestinal adaptation by stimulating endocrine signaling. Specifically, GLP-2, insulin-like growth factor 1 (IGF-1), insulin-like growth factor binding protein 3 (IGFBP-3), and growth hormone (GH) concentrations will be measured from blood samples before and after treatment with pancreatic enzymes. Plasma citrulline will also be measured as a marker of intestinal mass before and after treatment with pancreatic enzymes.

Test Article	Creon TM , a pancreatic enzyme preparation
Study Design	This study will characterize enteral absorption, including enteral fat absorption, in subjects with SBS. We propose a longitudinal study design to assess enteral absorption before and after pancreatic enzyme medication in subjects with SBS.

Inclusion and Exclusion:
INCLUSION CRITERIA
General Inclusion Criteria

- History of a small bowel resection
 - If small bowel resection occurred under 18 years of age, subjects must have dependence on parenteral nutrition for at least three months following small bowel resection
 - If small bowel resection occurred at 18 years of age or older, subjects must have 200 centimeters or less of residual bowel length and must have more than 3 bowel movements per day following small bowel resection
- Age 4 years to 75 years
- Usual state of health for the past two weeks with no medication changes
- Able to participate in a study for about four weeks with 2-4 study visits
- Able to take pancreatic enzyme medication orally

MBT/CCK Subset Inclusion Criteria

- Age 18 years to 75 years

All available details of estimated bowel length and presence or absence of an ileocecal valve will be taken into account, but there are no inclusion restrictions based on this information.

EXCLUSION CRITERIA
General Exclusion Criteria

- Significant disease other than SBS affecting the gastrointestinal tract that impacts absorption or digestion
- Motility disorders that affect the upper gastrointestinal tract (i.e. chronic pseudo-obstruction, severe gastroparesis) or motility disorders that are poorly controlled
- Unable to discontinue medications that directly alter fat absorption (i.e. bile acid sequestering agents, orlistat, weight loss medications, ursodeoxycholic acid) for one week prior to the first blood draw for the study until completion of stool collection following study visit 2 based on the preference of the subject or primary gastroenterologist. Permission must be obtained from the primary gastroenterologist before discontinuing medications in this category.
- Cholestatic liver disease defined as a serum conjugated bilirubin greater than 1.0 mg/dL), chronic renal failure requiring dialysis or listed for kidney transplant, or gout
- History of a pork allergy
- Candidate for intestinal transplantation and listed as status 1
- Women who are pregnant or lactating

	
 • History of fibrosing colonopathy 
MBT/CCK Subset Exclusion Criteria
 
 • History of a soy or safflower oil allergy
Number Of Subjects	
Non-MBT/CCK Subset: 16 subjects with SBS between the ages of 4 years and 17.9 years
 
MBT/CCK Subset: 10 subjects with SBS between the ages of 18 years and 75 years, subjects will have the option not to perform the MBT

Study Location	All study visits will occur at outpatient research offices at the Clinical and Translational Research Center of the Children's Hospital of Philadelphia (CHOP), a pediatric health care center.
Study Duration	Subject participation will last about 3-4 weeks.
Study Phases	
Study Visit 0: Informed consent, full 24 hour dietary recall if written consent obtained, blood draw if consent obtained and subject weighs less than 55 pounds, subjects may complete informed consent by telephone. If informed consent is obtained via telephone, then a signed informed consent form will be obtained either prior any study procedures, which includes a 24 hour dietary recall.
 
Study Visit #1: First study visit at CHOP. Subjects on pancreatic enzymes at baseline will have a three day washout period. Subjects who are not on pancreatic enzymes at baseline will not require a washout period. On the day of the study visit, all subjects will have laboratories drawn and anthropometrics. Those subjects in the MBT/CCK cohort will have a first MBT performed. Subjects who sign the informed consent form at visit 1 will complete a full 24 hour dietary recall instead of study visit 0. All subjects will be given instructions on how to complete a 3-day diet record and a 72-hour stool collection.
 
Study Visit #2: Following the initial diet record and stool collection, subjects can start pancreatic enzyme medication at study doses. Study visit #2 will be scheduled for day 5 of pancreatic enzyme medication. On the day of study visit #2, subjects will have laboratories drawn. Those subjects in the MBT/CCK cohort will have a second MBT performed. All subjects will complete a second 3-day diet record and a 72-hour stool collection at home. Following this, pancreatic enzyme medication will be discontinued and those subjects who were on pancreatic enzyme prior to the study will resume their regular dosing.
 
Study Visit #3: All subjects will provide their second 3-day dietary record and 72-hour stool collection. This visit will be used to ensure subject well-being and to monitor for adverse events. Subjects may complete this visit by telephone and mail stool samples to CHOP.

Efficacy Evaluations	The efficacy of pancreatic enzyme medication administration (Creon™) will be evaluated in subjects with SBS using CFA as the primary outcome. CNA and BC will be measured as secondary outcomes. Some subjects in the MBT/CCK cohort will also have the MBT as an outcome of the change in enteral fat absorption before and after pancreatic enzyme medication administration.

Pharmacokinetic Evaluations	N/A
Safety Evaluations	Safety will be monitored by adverse events reporting. The frequencies of AEs by type, body system, severity and relationship to study supplement will be summarized. SAEs (if any) will be described in detail.
Statistical And Analytic Plan	
The goal of the primary aim of the study is to compare the outcome CFA before and after pancreatic enzyme medication administration in subjects with SBS. The secondary outcomes of CNA and BC will also be compared in subjects with SBS before and after pancreatic enzyme medication administration. Descriptive statistics for CFA, CNA, and BC outcomes (mean, standard deviation, median, range, 95% CI) will be calculated for the SBS cohort before and after pancreatic enzyme medication administration with paired t-tests or Wilcoxon sign rank tests depending on skewness of data.
 
For the MBT outcomes, a moment-based pharmacokinetic (PK) analysis will be performed based on non-compartmental methodology using WinNonLin version 9.1 (Pharsight, Cary, NC). Baseline (C_0) and maximum (C_{max}) plasma concentrations are calculated, and area under the curve from time zero to eight hours (AUC) is calculated using the linear trapezoid method. PK parameters can then be compared between treatment groups using a paired t-test or Wilcoxon signed rank test as appropriate. To describe HA exposure relative to that of PA, the ratio of the HA to PA C_{max} (C_{max} HA/PA) and AUC (AUC HA/PA) is calculated for each subject after molar transformation and dose-normalization of exposure metrics⁷. Alternately, population PK analyses for repeated-measures endpoints can be conducted via nonlinear mixed-effects modeling with a qualified installation of the nonlinear mixed-effects modeling (NONMEM) software, Version VII, Level 2.0 (ICON Development Solutions, Hanover, MD⁸. Using this method, population PK modeling is conducted by simultaneously fitting structural PK models to both PA and HA concentrations⁹.
 
Descriptive statistics (mean, standard deviation, median, range, 95% CI) will also be employed to assess outcomes related to intestinal hormone signaling that controls pancreatic enzyme secretion and intestinal adaptation in H4 (glucagon-like peptide 2, insulin-like growth factor 1, insulin-like growth factor binding protein 3, and growth hormone concentrations). All variables will be tested for normality and nonparametric tests used as appropriate. The change in status for these variables before and after pancreatic enzyme medication administration will be explored with paired t-tests and Wilcoxon sign rank tests depending on skewness.


MONITORING PLAN

The Principal Investigator, [name], is ultimately responsible for monitoring data integrity, patient safety, and overall study oversight. The study will be monitored weekly by the PI and [name]. The study protocol will be carried out in accordance with OHRP guidelines and requirements. SAEs that are unanticipated, serious, and possibly related to the study will be managed by the PI, [name], as well as her mentor ([name]). For subjects with SBS primarily managed at CHOP, members of the Intestinal Rehabilitation Program ([name]) will be consulted immediately for all SAEs. For subjects with SBS primarily managed at Penn Medicine/HUP, their primary gastroenterologist and co-investigator, [name], will be consulted immediately and will assume medical care. SAEs will be reported to the study sponsor, IRB, CTRC, and all members of the research team in accordance with requirements. Anticipated SAEs or those unrelated to the study will be reported to the same individuals/entities in accordance with requirements. There will be ongoing collection of data on adverse events and compliance to the treatment protocol throughout the study by the PI, [name], which will be reviewed weekly by [name].

SCHEDULE OF STUDY PROCEDURES & STUDY TIMELINE

Table 1. Summary of Study Visits #1 and #2 and Methods

	All subjects	MBT/CCK Subset		Non-MBT/CCK Subset		All subjects
		Visit 1	Visit 2	Visit 1	Visit 2	
Assessment	Visit 0					Visit 3
Obtain informed consent	•					
Study Intervention: Administration of Creon™			•		•	
Primary Outcome						
Coefficient of Fat Absorption (stool)		•	•	•	•	
Secondary Outcomes						
Coefficient of Nitrogen Absorption (stool)		•	•	•	•	
Fecal Bomb Calorimetry (stool)		•	•	•	•	
Malabsorption Blood Test (MBT) (PA, HA, HA/PA absorption, pharmacokinetics)		• [#]	• [#]			
Serum prealbumin		•	•	•	•	
Intestinal Adaptation: serum citrulline, IGF-1, IGF BP3, GLP 2, GH, stool pH, gastric pH		•	•	•	•	
Serum CCK		• [#]	• [#]			
Fecal elastase		•		•		
Diet						
24-hour dietary recall	•	• ^{**}				
3-day Weighed Food Record		•	•	•	•	
Safety						
Complete Blood Count with Differential		•	•	•	•	
Serum Basic Metabolic Panel		•	•	•	•	
Serum Hepatic Function Panel		•	•	•	•	
Adverse Event Monitoring		•	•	•	•	•
Other						
Anthropometry: height, weight, DXA, skinfolds, circumferences		•		•		
Nutrition Labs: serum vitamins A, E, K; 25-OH vitamin D; zinc; selenium; fatty acid profile	• [*]	•		•		
Health History and Medications		•		•		
Home Environment Questionnaire		•		•		
Pancreatic enzyme medication adherence			•		•	•
Quality of life (MOS SF-36 for adults, PedsQL for subjects < 18 years)		•		•		

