Goulet et al²¹ demonstrated improved absorption and decreased dependence on parenteral nutrition following treatment with growth hormone. These patients had increased plasma levels of citrulline, a measure of total intestinal mass, as well as increased serum IGF-1 and insulin-like growth factor binding protein 3 (IGFBP-3) concentrations in association with growth hormone (GH) therapy.

In our proposed study, we will explore how improved nutrient absorption alters intestinal adaptation and enteric hormone secretion. We will measure baseline GLP-2, IGF-1, IGFBP-3, GH, and citrulline serum levels. Following administration of pancreatic enzymes, we will assess if improved digestion of nutrients promotes intestinal adaptation by stimulation of enteroendocrine cells. This would be reflected in an increase in serum levels of GLP-2, IGF-1, IGFBP-3, GH, and citrulline following exposure to pancreatic enzyme medication.

As outlined above, rapid intestinal transit, high intestinal luminal volume that may dilute pancreatic enzymes, acid hypersecretion, and altered enteroendocrine hormone secretion all serve as likely causes of functional pancreatic insufficiency in patients with short bowel syndrome. In the proposed study, we will measure fat absorption in subjects with SBS at baseline and following exposure to pancreatic enzyme medication. If treatment with pancreatic enzymes results in improved enteral absorption, it could allow parenteral nutrition to be decreased. This may substantially improve morbidity and mortality in patients with SBS. Furthermore, pancreatic enzymes are a noninvasive intervention with a good safety profile in other disease processes. It would be easy to incorporate their use into the clinical care of patients with SBS if there was evidence that pancreatic enzymes improve enteral absorption.

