Descriptive statistics (mean, standard deviation, median, range, 95% CI) will also be employed to assess outcomes related to intestinal hormone signaling that controls pancreatic enzyme secretion and intestinal adaptation in **H4** (glucagon-like peptide 2, insulin-like growth factor 1, insulin-like growth factor binding protein 3, and growth hormone concentrations). All variables will be tested for normality and nonparametric tests used as appropriate. The change in status for these variables before and after PERT administration will be explored with paired t-tests and Wilcoxon sign rank tests depending on skewness.

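### The exploratory adaptation aim asks about improved absorption, but H4 is analysed only as before-versus-after change in each marker and is never related to the change in absorption

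*Combined protocol and SAP*

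**What the plan says.** **The aim.** The synopsis (Study Objective(s)) says that "we will explore the effect that improved nutrient absorption will have on intestinal adaptation by measuring changes in markers", going on to name intestinal mass and hormone levels. Section 1.5 repeats that "we will explore how improved nutrient absorption alters intestinal adaptation and enteric hormone secretion". Section 2.2.1 again names improved nutrient absorption, and section 2.2.3 names improved lipid digestion.

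**The hypothesis.** H4 in the synopsis reads: "By promoting lipid digestion and release of free fatty acids, pancreatic enzymes will promote intestinal adaptation by stimulating endocrine signaling". Section 1.5 gives the expected direction: "This would be reflected in an increase in serum levels of GLP-2, IGF-1, IGFBP-3, GH, and citrulline following exposure to pancreatic enzyme medication".

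**The analysis.** The synopsis says: "The change in status for these variables before and after pancreatic enzyme medication administration will be explored with paired t-tests". Section 6.3.1 Efficacy Analysis says the same: "The change in status for these variables before and after PERT administration will be explored with paired t-tests and Wilcoxon sign rank tests", the choice depending on skewness. Both places list GLP-2, IGF-1, IGFBP-3 and GH. Citrulline is absent from both lists, although H4 and sections 2.2.3 and 6.2 include it.

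**Other planned associations.** Section 6.3.1 plans plots, correlation and regression of MBT metrics against CFA% and BC. No adaptation marker enters them. Section 6.3 mentions scatter plots, but to look for skew and outliers.

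**Design.** Sections 3.2 and 9.1 describe an open-label, non-randomised study in which every subject receives Creon.

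**The concern.** The exposure in the aim is improved absorption or digestion. The exposure in the analysis is Creon on versus off. These differ whenever Creon does not improve absorption in every subject, and whether it does so at all is the primary question of the trial.

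A paired test of GLP-2 or citrulline gives the same result whether the rise sits in the subjects whose CFA rose or in those whose CFA did not. With no control arm, a shift between the two visits may also have causes unrelated to Creon. The planned output therefore supports a statement about change on Creon. It does not support a statement about change that accompanies better absorption, which is what the aim asks. Each subject supplies both a marker change and a CFA change, so the data to look at this exist; the plan simply does not pair them.

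**Working it through.** **1. The plan's own figure.** Section 6.4: 22 subjects, mean CFA difference 9%, SD of differences 14%, two-sided 0.05, 80% power. Paired t-test by the noncentral t: df = 21, noncentrality = (9/14) × √22 = 0.643 × 4.690 = 3.02. Power is 82.0% at n = 22 and 80.0% at n = 21. The stated figure is reproduced to within two points.

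**2. What the paired marker test can distinguish.** Assumptions, not taken from the documents: n = 22, a marker shift of 0.643 SD (the same standardised size as the CFA calculation), and marker change independent of CFA change. Results of 40,000 simulated trials:

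| True mean CFA change | Marker test significant | CFA test significant | Marker significant, CFA not | Correlation of changes significant |
|---|---|---|---|---|
| 0 | 82% | 5% | 78% | 5% |
| 0.643 SD | 82% | 82% | 15% | 5% |

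The marker result is 82% in both rows: it carries no information about absorption. The 78% is 0.82 × 0.95. Reading the mean CFA change beside the marker separates the two rows. It does not show whether the same subjects changed on both, and the correlation is the quantity that addresses this.

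**3. What a correlation of changes would give.** Section 3.3.2 expects 26 enrolled and at least 22 evaluable. Fisher z, SE = 1/√(n − 3) = 1/√19 = 0.229 at n = 22.

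- Detectable r at 80% power: tanh[(1.960 + 0.842)/√19] = tanh(0.643) = 0.57. At n = 20 it is 0.59 and at n = 26 it is 0.53.
- Power at assumed true r of 0.3, 0.4, 0.5 and 0.6: 27%, 46%, 67% and 86%.
- 95% CI = tanh[atanh(r) ± 1.96/√19]. For r = 0.3: tanh(0.310 ± 0.450) = -0.14 to 0.64. For r = 0.5: tanh(0.549 ± 0.450) = 0.10 to 0.76.

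These are Pearson-type approximations, so treat them as a guide to the precision of Spearman's r.

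**4. Are the pairs comparable?**

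- Timing: on treatment, blood is drawn on day 5 and stool collected on days 8 to 10 (section 4.4). Off treatment, blood is drawn on day 8 and stool collected on days 11 to 13 (section 4.2). The lag is three days in both periods, so the two changes are aligned with each other but not simultaneous.
- GLP-2: subjects following the non-MBT protocol give one sample on their normal diet. MBT subjects give a fasting pre-meal sample and further samples at 1 and 2 hours. The two subsets differ in feeding state, so a pooled plot needs a stated choice of sample.

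**The case against.** The strongest reply is that the plan does test H4 as H4 is operationalised. The subject of H4 is the enzymes, the synopsis objective says that its method is measuring marker changes, and sections 2.2.3 and 6.2 describe measurement before and after. The paired test answers that question. This stands for the total change on Creon. It does not cover the absorption part of the aim, which the protocol states more than once.

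A second point also stands. H4's pathway is luminal: section 1.5 explains that free fatty acids and monoacylglycerols act on receptors to release hormones such as GLP-2. CFA measures net fat absorption, not lipolysis. In resected bowel, lipolysis could rise with little gain in CFA, and H4 would still predict a hormone rise. A rule that credits H4 only when CFA improves would therefore be wrong. The more lipolysis-specific measure, the MBT contrast of triglyceride with free fatty acid, is available in at most 10 adults.

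Third, a reader might infer from section 1.5 that any marker rise will be credited to absorption even if CFA did not move. The documents do not say so. The sentence sits in the literature background and gives the direction expected if the hypothesis is true; section 6 contains no such decision rule. CFA is the primary outcome, so a null CFA would be in plain view. Nor is the correlation the only evidence on the question: the mean changes in CFA, CNA, BC and MBT bear on it too.

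Finally, a correlation across some 22 subjects in one arm does not prove mediation. A correlation near zero would not exclude it either, for instance if all subjects responded alike.

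**Conclusion.** The gap is real and of low severity. The aim refers to improved absorption or digestion, the H4 analysis uses only before-versus-after marker change, and no section links the two. In this single-arm design the planned result can show change on Creon, but not whether that change accompanies better absorption.

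No number in the plan is wrong on this point. An added correlation would be imprecise: at 22 pairs, 80% power needs r of about 0.57, and r = 0.3 has a 95% CI of about -0.14 to 0.64. These figures assume that all 22 evaluable subjects have both changes; separate GLP-2 subsets would be less precise still. Several markers would be examined, so an isolated large r should be read cautiously. This supports estimation in an exploratory aim and no more.

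**What to change.** In the synopsis (Statistical And Analytic Plan) and section 6.3.1 Efficacy Analysis, add for H4:

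- For each of GLP-2, IGF-1, IGFBP-3, GH and citrulline, plot the within-subject change against the within-subject change in CFA, and report Spearman's r with its 95% CI. Name citrulline explicitly, since the present H4 analysis text omits it.
- For GLP-2, use the single visit sample in subjects on the non-MBT protocol and the pre-meal baseline sample in MBT subjects. Show the two subsets separately because of their different feeding state.
- State that a before-versus-after rise alone is reported as change on Creon. A rise without CFA improvement is not described as an effect of improved absorption, although it does not rule out H4's luminal-digestion pathway.
- State that the analysis is exploratory and for estimation, with no significance threshold and no pass/fail rule for attribution.
- Record the limits: about 22 pairs, several markers, blood drawn three days before stool collection starts in each period, and no proof of mediation.

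The cost is a few lines of text and one plot per marker (two panels for GLP-2). No visit, sample or assay is added. It parallels what section 6.3.1 already plans for the MBT.
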